Outcome(s):	
The primary endpoint of this clinical trial is the incidence rate of postoperative hypersensitivity. The assessment of the postoperative hypersensitivity is performed and graded according to the FDI criteria (Hickel et al. 2007; Hickel et al. 2010, Hickel et al. 2022).
 
The secondary outcomes are the vitality and fracture rate of restored teeth and the retention/fracture rate of restorations. These parameters provide information about the clinical performance of the bond of the restoration to the tooth structure. Another secondary outcome is the marginal quality of the restorations that also provides information about the quality of the bond between tooth structure and luting composite. The secondary outcomes will be assessed at all recalls with the respective FDI criteria (Hickel et al. 2022).

Design:	
This is a prospective single-arm clinical investigation. The safety and performance results of ██████████ will be compared with the coded data of the control group (Adhese Universal) of an already performed clinical investigation ("Clinical evaluation of a new dual cure universal adhesive (Adhese Universal DC) in the indirect restorative therapy: A randomised, controlled clinical trial", NCT04475679). The study design of the planned clinical investigation follows the design of the previously conducted clinical investigation. The objectives, outcome parameters and methods are the same.

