2.2 Primary Objective

The investigation seeks primarily to determine the rate of postoperative hypersensitivity occurrence after using [REDACTED] for the placement of indirect restorations. The results will be compared to the control group (Adhese Universal) of a previously conducted clinical investigation.

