6.1 Hypothesis

The null hypothesis is that there is a statistically significant difference between control and test group with respect to postoperative hypersensitivity.

The alternative hypothesis is that there is no difference between control and test group with regard to postoperative hypersensitivity.

We do not expect in this equivalence study to find any statistical significance between control and test group with regard to postoperative hypersensitivity.

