6.2 Determination of Sample Size

The number of samples estimated to be needed for each study arm is 40 to achieve the objective. The G*Power sample calculator software Version 3.1.9.2 was used to determine the sample size, at a power of 80% and a type I error of 0.1 (Faul et al., 2007; Faul et al., 2009).

Different to the previous study, this time a drop-out of 5 restorations is assumed. Therefore, the sample size aimed at is 45 instead of 40.

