6.4.2 Primary Analysis

Regarding the primary outcome, the interim analysis will be done at baseline. The final analysis of the primary outcome will be done after completion of the 1-month recall. The analysis will be done by the principal investigator within 3 months after the collection of the 1-month data.

A non-parametric test (Mann-Whitney) between two independent groups will be used to compare the level of postoperative hypersensitivity (FDI 11) between the control and the test group.

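### The primary endpoint is an incidence rate, but the only planned primary analysis is a Mann-Whitney test on FDI grade, which estimates no rate and has little power for a mild-to-serious shift at equal incidence

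*Combined protocol and SAP*

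**What the plan says.** The synopsis (Outcomes) states: "The primary endpoint of this clinical trial is the incidence rate of postoperative hypersensitivity". It adds that hypersensitivity is graded by the FDI criteria. Section 2.2 sets the same target: "The investigation seeks primarily to determine the rate of postoperative hypersensitivity occurrence", to be compared with the control group of the previous trial.

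Section 6.4.2 names one method: "A non-parametric test (Mann-Whitney) between two independent groups will be used to compare the level of postoperative hypersensitivity (FDI 11". On timing it says "The final analysis of the primary outcome will be done after completion of the 1-month recall", after an interim look at baseline. Section 6 does not say which grade counts as an event, and it plans no proportion, difference in proportions or confidence interval for the primary outcome. The descriptive analysis in section 6.4.3 is for the secondary outcomes.

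On how the result will be read, section 6.1 says: "We do not expect in this equivalence study to find any statistical significance between control and test group". No margin is given.

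**The concern.** A rank test on a five-step grade answers a different question from the one posed. It asks whether teeth in one cohort tend to have higher grades than teeth in the other. It does not say how many teeth became hypersensitive, by how much the cohorts differ, or how precisely either is known. A sponsor who follows section 6.4.2 to the letter will not have determined the rate.

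The second issue is what the p-value can detect. In the section 3.1 table, grade 2 needs no treatment, while grade 4 means replacement of the restoration or endodontic treatment. Ranks record only the order of these grades, not the distance between them. If few teeth are symptomatic, a move of those teeth from grade 2 to grade 4 barely changes the statistic. In a study that treats absence of significance as the desired finding, such a result could be reported as no difference on the primary endpoint of a pivotal investigation.

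**Working it through.** **The plan's own figure.** Section 6.2 gives "The number of samples estimated to be needed for each study arm is 40 to achieve the objective", "at a power of 80% and a type I error of 0.1". This cannot be reproduced, because no effect size, control rate, margin or sidedness is stated. The drop-out step does reproduce: 40 + 5 = 45. The checks below use 40 per group.

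**Inputs.** n = 40 per group and alpha = 0.1 come from section 6.2, and the meaning of the grades from the section 3.1 table. The grade counts are illustrative. Alpha is taken as two-sided and teeth as independent.

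**Step 1: what the method delivers.**

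| Needed for the endpoint | Planned in section 6? |
|---|---|
| Event grade | No |
| Proportion per cohort | No |
| Difference, test minus control | No |
| Confidence interval | No |
| p-value on grade ranks | Yes (6.4.2) |

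This step needs no assumed counts.

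**Step 2: severity shift at equal incidence.** Control: 32 teeth at grade 1 and 8 at grade 2. Test: 32 at grade 1 and 8 at grade 4.

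- U counts the test-control pairs in which the test tooth is worse, with ties as one half: 8 × 40 + 0.5 × 32 × 32 = 320 + 512 = 832. The null value is 40 × 40 / 2 = 800.
- The tie-corrected variance is (n₁n₂/12) × [(N + 1) − Σ(t³ − t)/(N(N − 1))], with tie groups of 64, 8 and 8. Σ(t³ − t) = 262,080 + 504 + 504 = 263,088. The variance is (1600/12) × (81 − 263,088/6,320) = 5,249.6, so SD = 72.45.
- z = (832 − 800)/72.45 = 0.44, p = 0.66.

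The whole shift adds 8 × 8 / 2 = 32 to U. Grade 3 or grade 5 in place of grade 4 would give the same U.

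For the same teeth, grade 4 or worse is 0/40 against 8/40: difference 20 points, Newcombe 95% CI 7 to 35, Fisher p = 0.005.

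| Symptomatic, each group | Mann-Whitney p | Fisher p, grade 4 or worse |
|---|---|---|
| 4 v 4 | 0.88 | 0.116 |
| 6 v 6 | 0.78 | 0.026 |
| 8 v 8 | 0.66 | 0.005 |

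**Step 3: power.** With a true 20% symptomatic in both groups, control cases all grade 2 and test cases all grade 4, power at 0.1 is about 13 to 14% for the Mann-Whitney and 92% for Fisher on grade 4 or worse. Only about 11% is rejection in the direction that shows the test product as worse.

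**Step 4: counter-check, serious cases added from grade 1.** Control: 40 at grade 1. Test: 36 at grade 1 and 4 at grade 4. U = 4 × 40 + 0.5 × 36 × 40 = 880, SD = 39.23, z = 80/39.23 = 2.04, p = 0.041. Fisher on grade 4 or worse gives 0.116, so here the rank test is the more sensitive of the two.

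**Step 5: does any-grade incidence alone repair step 2?** No. In the 8 v 8 case it is 20% in both groups: difference 0 points, 95% CI −18 to +18. A severity result is needed beside it.

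**The case against.** Three arguments have weight.

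- **The outcome is graded, so a rank test is a legitimate comparison.** This stands. The fault is that it is the only primary analysis, not that it appears at all. A reader might infer that the test cannot see the serious grades. Step 4 shows that it can when serious cases add to the total. The near-blindness is confined to worsening among teeth that would be symptomatic anyway.
- **Other parts of the plan would reveal severe cases.** This stands in part. Adverse events are recorded throughout, and vitality and retention are described as secondary outcomes, so the documents do not support a claim that severe cases would go unnoticed. Section 6.3 would stop the study for more than 5 teeth above grade 3, a count that the 6- and 8-case examples exceed. But that rule applies only before baseline, the other rule concerns grade 5 in more than 20% of restorations, and neither compares with control. Control 6/40 at grade 2 against test 5/40 at grade 4 stays within the limit of 5, and the Mann-Whitney gives p = 0.94.
- **The illustrations are extreme.** They put all control cases at one grade and all test cases at another. This is fair: they show a mechanism and do not forecast the result. Step 1 does not depend on them.

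Reading non-significance as equivalence without a margin is a separate weakness, in section 6.1. It makes this point matter more but does not create it.

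**Conclusion.** The concern holds in two parts of different strength. First, and without any assumption, the plan contains no analysis that estimates its stated primary endpoint or the difference from control, so this must be fixed before the comparison is made. Second, conditional on most teeth being at grade 1, the Mann-Whitney has almost no power for a shift from mild to serious grades at equal incidence: about 13 to 14% at the 0.1 level with 20% symptomatic in both groups, against 92% for the proportion at grade 4 or worse.

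The second part rests on assumed control rates, two-sided testing and independent teeth. Up to two teeth per participant are allowed, so intervals that respect clustering would usually be wider than those shown. The documents do not support a reading that the test misses serious grades in general, or that the trial will reach a wrong conclusion. They show that a worse severity profile could yield the hoped-for non-significant result with no planned estimate beside it.

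**What to change.** Amend section 6.4.2 before the cohorts are compared. The control trial has already been performed, so a cut-point chosen later would be open to challenge.

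1. Define the event, for example FDI 11 grade 2 or worse.
2. Define the time point, for example the 1-month recall or the worst grade up to it. Reconcile this with section 3.1, which already uses the highest grade for teeth that do not settle or that worsen after treatment.
3. Apply one rule to tooth-level coded data from both cohorts.
4. Make the primary analysis the proportion with an event in each cohort with an exact CI, and the test-minus-control difference with a CI that allows for up to two teeth per participant.
5. Pre-specify the same difference and CI for grade 4 or worse, reported alongside the primary result.
6. Keep the Mann-Whitney as supportive.

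The cost is SAP wording and a few tables. No new test-cohort data are collected, but tooth-level control records with a participant code must be available. The downside is that the intervals will look wide: 4/40 is 10% with an exact 95% CI of 3% to 24%. That imprecision exists under the current plan too, but a lone p-value does not show it.

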6.4.3 Secondary Analyses

Regarding the secondary outcomes, the analysis will be done after completion of the 1, 6, 12, 24, 36 and 60 months recall examinations, respectively. The analysis will be done by the principal investigator within 3 months after the collection of the baseline data. It will be a descriptive analysis.

6.4.4 Interim analyses

The interim analysis will be done after the collection of data of the 6, 12, 24, 36 and 60 months recall examinations of all restorations. The analysis will be done by the principal investigator within 3 months after the collection of the recall data. In case of any further therapy related to the restorative intervention the restoration maybe regarded either as failure or as drop-out. Stopping guidelines are not necessary since the restorations are final interventions.

No adjustment methods are needed for this clinical study since the interim analysis are for safety stopping reasons only.

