2.4 Safety Objectives

The safety objectives are already covered in the primary and secondary objectives. This study aims to assess the long-term safety of [REDACTED] in terms of tooth vitality and failure rate of the placed restorations. Tooth vitality is an indicator for the health status of the dental pulp. A vitality test is performed to acquire information about the vitality of teeth before and after the treatment. A healthy dental pulp offers a positive response to the vitality test. Once the dental pulp is injured an irreversible inflammatory reaction starts with a possible necrosis of the dental pulp. Pulpal necrosis is followed by a negative response to the vitality test.

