3.4 Safety Outcomes

No other specific safety outcomes than the previous described (postoperative hypersensitivity, loss of vitality, loss of restoration, tooth fracture, tooth loss) will be evaluated. No laboratory parameters or other measurement or devices come to use in this clinical trial.

4.. CLINICAL INVESTIGATION DESIGN

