6.3 Statistical criteria of termination of the investigation

The study will be terminated if more than 20% of the restorations fail (FDI grade 5 on any of the criteria).

The study would be terminated prior to reaching baseline if more than 5 treated teeth were found to have post-operative hypersensitivity (FDI 11 >grade 3).

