6.4.1 Datasets to be analysed, analysis populations

The data collected of all eligible participants that received a final restoration will be used for the statistical data analysis.

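### Section 6.4.4 allows a restoration needing treatment-related further therapy to be classed as a drop-out, which can understate the failure rate and overstate retention

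*Combined protocol and SAP*

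**What the plan says.** Section 2.4 sets a long-term safety aim "in terms of tooth vitality and failure rate of the placed restorations". Section 3.4 closes the safety list with this sentence: "No other specific safety outcomes than the previous described (postoperative hypersensitivity, loss of vitality, loss of restoration, tooth fracture, tooth loss) will be evaluated". Section 3.2 makes vitality, marginal hard-tissue defects and retention or fracture secondary outcomes, and Section 6.4.3 analyses them descriptively.

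For restorations that need more treatment, Section 6.4.4 says: "In case of any further therapy related to the restorative intervention the restoration maybe regarded either as failure or as drop-out". The sentence before it assigns the work: "The analysis will be done by the principal investigator within 3 months after the collection of the recall data".

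Three other places bear on the rule:

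- Section 6.3 gives the only explicit meaning of failure, inside a termination rule: "The study will be terminated if more than 20% of the restorations fail (FDI grade 5 on any of the criteria".
- Section 6.4.1 defines the analysis set: "The data collected of all eligible participants that received a final restoration will be used for the statistical data analysis".
- Section 6.5 says when drop-outs are replaced and allows for 5 of them. It does not define a drop-out or say how one enters a rate.

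Section 6.4.4 also says "Stopping guidelines are not necessary since the restorations are final interventions", and then "No adjustment methods are needed for this clinical study since the interim analysis are for safety stopping reasons only".

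**The concern.** The sentence concerns therapy already accepted as related to the intervention, so the event is informative about the adhesive. A drop-out label treats it as if it were not. Because no criterion is given, the label can be chosen at analysis, once the outcome is known.

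What is at stake is the reported failure rate and, in mirror image, retention over 60 months. The trial is pivotal and serves conformity assessment, and the synopsis and Section 4.1 set its results beside the control group of an earlier trial. A rate that depends on unexplained labels is hard to defend there.

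A minor editorial matter sits in the same section. It calls stopping guidelines unnecessary although Section 6.3 contains two termination rules, and it then describes the interim analyses as serving safety stopping only.

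**Working it through.** **Does another section close the gap?**

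- *Section 6.3.* Grade 5 is the failure definition for termination, and Section 6.4.4 does not refer to it. In the hypersensitivity table of Section 3.1, replacing the restoration, or endodontic treatment through an access cavity alone, is grade 4. Those cases remain open.
- *Section 3.1.* The rule that the highest FDI value is analysed covers hypersensitivity, not retention, fracture or margins.
- *Section 6.4.1.* It points to a fixed denominator but does not say that a case labelled drop-out counts as a failure.
- *Sections 6.4.3 and 6.5.* Neither names an estimator, a censoring rule or a definition of drop-out.

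None of them settles the classification.

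**Size.** The plan's own figure reproduces: 40 restorations plus 5 assumed drop-outs = 45 (Sections 6.2 and 6.5). The documents give no expected failure rate, so the failure counts below are assumptions. Let N = 45, F = true failures, and k = failures labelled drop-out. The plan does not say whether drop-outs leave the denominator, so both versions are shown. Retention is taken as the complement of failure, which is a simplification.

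Assumed F = 5:

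| k | Failure, case removed: (F−k)/(N−k) | Failure, fixed denominator: (F−k)/N | Retention, case removed: (N−F)/(N−k) |
|---|---|---|---|
| 0 | 5/45 = 11.1% | 5/45 = 11.1% | 40/45 = 88.9% |
| 1 | 4/44 = 9.1% | 4/45 = 8.9% | 40/44 = 90.9% |
| 2 | 3/43 = 7.0% | 3/45 = 6.7% | 40/43 = 93.0% |

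Assumed F = 2: 2/45 = 4.4% becomes 1/44 = 2.3% (1/45 = 2.2% fixed) after one, and 0% after two.

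Each relabelled case therefore moves the failure rate down, and retention up, by about 2 points.

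**Against sampling error.** Exact (Clopper-Pearson) 95% intervals are 3.7% to 24.1% for 5/45 and 2.5% to 21.7% for 4/44. They treat restorations as independent, although a participant may contribute two.

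**Termination rule.** This is touched only if relabelled cases are also left out of the grade-5 count. The rule needs more than 20%: 10/45 = 22.2% triggers. With a fixed denominator one relabelled case avoids the trigger (9/45 = 20.0%). With removal, 9/44 = 20.5% still triggers and two are needed (8/43 = 18.6%).

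**Choice of denominator for the fix.** Dividing by all restorations placed would count those lost to follow-up as successes. With 5 failures and the plan's 5 drop-outs, that gives 5/45 = 11.1%, against 5/40 = 12.5% when the denominator is the 35 still evaluated plus the 5 earlier failures.

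**The case against.** The best defence is that little is hidden. Secondary outcomes are graded on FDI criteria at the recalls and adverse events are collected throughout, so the event stays on record whatever label is added. Under Section 4.2.3 the evaluators place no restorations and are not told who the operator was. The affected analyses are descriptive, and Section 3.1 largely protects the primary endpoint. All of this stands and limits the seriousness. It does not say how the case enters the failure rate.

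Several stronger readings are tempting but not supported:

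- *The rule can err in one direction only.* Applying the drop-out option to a true failure always lowers the rate. But the sentence covers any related therapy, so fluoride varnish could be called a failure, which would raise it. The rule as a whole is undefined rather than one-sided.
- *The comparison with the control group would reverse.* With 5/45 and one relabelled case, the only count out of 40 that falls between the two rates is 4/40 = 10.0%. With 3/40 = 7.5% or 5/40 = 12.5% nothing reverses. The documents give no control count.
- *The two data sets were labelled differently.* Section 6 says the methodology and endpoints are the same. How the earlier trial used its labels is not shown.
- *The option breaches the rule in Section 3.1 that doubtful cases receive the higher score.* That rule is about FDI grading, not failure versus drop-out.
- *The termination rules are cancelled by Section 6.4.4.* Section 6.3 still stands; the conflict is one of wording.

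**Conclusion.** The concern holds. The plan expressly permits a treatment-related failure to be classed as a drop-out, and no other section prevents it. If the option is used for a true failure, the descriptive failure rate is understated and retention overstated, by about 2 percentage points per case with 45 restorations.

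The size rests on assumed failure counts. The direction is the same whether or not drop-outs leave the denominator. The bias is possible, not certain: nothing in the documents shows that the option would be used to improve the result. It is also smaller than sampling error, although a confidence interval would not reveal it. It should be corrected because the failure rate is a named safety measure and the correction is cheap. It does not undermine the primary analysis.

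**What to change.** In Section 6.4.4, delete the drop-out alternative and state that:

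- restoration-related replacement, repair, endodontic treatment, loss of the restoration or loss of the tooth is a failure from that date; endodontic treatment with the restoration left in place is also shown separately under vitality;
- fluoride varnish or repolishing alone is not a failure;
- drop-out means withdrawal or loss to follow-up unrelated to the restoration, and uncertain cases count as failures;
- each recall reports cumulative failures over restorations evaluated at that recall plus earlier failures, or a Kaplan-Meier estimate with unrelated drop-outs censored, with the number lost shown;
- the same definition is applied to the control data, or the report states as a limitation that the coded data do not allow it.

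In Section 6.3, add that any recorded FDI grade 5 counts towards termination whatever its later label. The thresholds stay as they are. This count remains narrower than the failure definition above, because replacement alone can be grade 4.

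As an editorial change, replace the sentence in Section 6.4.4 about stopping guidelines with a reference to Section 6.3.

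The cost is wording in two sections and no extra visits. The reported failure rate may be slightly higher, and the control data may need re-coding; the documents do not show whether that is possible.

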6.4.5 Deviation(s) from the original statistical plan

Deviations from the original statistical plan must be reported to the sponsor.

6.5 Handling of missing data and drop-outs

If a participant withdraws before all baseline examinations are completed, he/she will be replaced by another participant. Once all baseline examinations are completed, drop-outs are no longer replaced. There have only been few drop-outs and no-shows in the internal clinic in previous clinical trials so far. However, a drop-out of 5 restorations was assumed. Therefore, 45 instead of 40 restorations will be placed.

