Measurements and procedures:	
After information and written informed consent the participants will receive a dental treatment in relation to the restorative indication (caries, tooth/restoration fracture, insufficient restoration, etc), which means that the inlay/onlay cavity will be prepared and a digital impression with an intraoral scanner (Trios 3Shape) will be taken. Then, the cavities will be temporarily restored with provisional restorations. The scans will be sent to the lab where dental technicians will provide the final restorations made of lithium disilicate e.max CAD. In the following appointment the final restorations will be luted and final corrections as well as the finishing and polishing procedures will be done.
 
The baseline recall will take place 6-12 days after the insertion of the restoration. At the baseline recall the study specific parameters will be evaluated according to the FDI criteria ranging from 1 excellent to 5 clinically not acceptable.
 
Further recalls will be performed at 1, 6, 12, 24, 36 and 60 months after placement of the restoration.

Intervention:	
After getting a tooth which is in a need of a restoration (inlay or onlay), the cavity will be prepared, and an optical impression is taken. Then provisional restoration is cemented during the time, which is necessary to produce the indirect restoration in the dental lab. This first treatment appointment takes around 2.5 h. In a second treatment appointment the indirect ceramic restoration is luted to the tooth surface by the investigational product [REDACTED] and the well-established luting composite Variolink Esthetic DC. This will take at maximum 2 hours. During the baseline appointment a repolish of the restoration can be done by the operator before the evaluator assesses the restoration and the tooth. This will take at maximum 30 minutes. All following recall visits will take no longer than 30 minutes.

Control intervention (if applicable):	n.a.
Number of subjects with rationale:	45 teeth, at maximum two teeth per participant according to the statistical considerations.
Duration of the investigation:	5 years

Investigation schedule:	October 2024 First- subject –In (planned) April 2031 of Last- subject –Out (planned)

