3. CLINICAL INVESTIGATION OUTCOMES

3.1 Primary Outcome

Postoperative hypersensitivity is considered an indicator of the response of a tooth (pulp) to the therapeutic procedure applied. Postoperative hypersensitivity can be observed within a short time after the treatment. Therefore, it is assessed for the first time at the baseline recall (after 6-12days). The assessment of postoperative hypersensitivity includes questions about type and duration of pain, intensity of pain and on the stimulus inducing the pain (Hickel et al. 2007, Hickel et al. 2010, Hickel et al. 2022). The subjective perception of the intensity of postoperative hypersensitivity caused by thermal stimuli and caused by occlusal forces (during biting) will be determined by the aid of a Visual Analog Scale (VAS). The VAS values are brought into relationship to the preoperative values. In the table below a description of the correlation between FDI grade and VAS values and clinical signs and symptoms is shown. Not all signs need to be present at one stage. The exact VAS values vary widely from patient to patient, depending on each individual's pain tolerance. Therefore, it is one of the factors influencing the FDI grade, but it is not directly correlated. Not all the described conditions have to be fulfilled to attribute an FDI score. Depending on the intensity and character of the pain, further therapy will be determined. Usually, postoperative hypersensitivity subsides spontaneously, and no treatment is necessary. In case of very intense pain an immediate treatment is required. The application of a fluoride varnish is the first procedure of choice. If no improvement is achieved by this method, then the replacement of the restoration would be the next step. In the worst case, the pulp is severely inflamed, requiring endodontic treatment. If the postoperative hypersensitivity does not subside spontaneously or worsens after the applied treatment, the highest assessed FDI value is used for the statistical analysis.

For all participants a 1-month recall is planned to finally assess the postoperative hypersensitivity. The clinical experience of the evaluator is of major importance in the correct assessment of the FDI grade. In general, the rule applies, that in case of uncertainties the higher score is attributed.

FDI grade	1	2	3	4	5

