4.1 General clinical investigation design and justification of design

████████ a new dental adhesive will be used to lute 45 inlays or onlays out of e.max CAD to teeth of at least 23 patients.

This prospective study has only one group (████████) because the planned study is similar to a trial which has recently been executed in the internal clinic of Ivoclar Vivadent AG (NCT04475679). The only difference to the already performed study is the device under assessment. Therefore, the coded results of the control group of the previous clinical investigation (Adhese Universal) will be compared with the clinical performance of the new dental adhesive (████████).

There are 5 operators and 2 evaluators. All operators are very experienced dentists in the field of restorative dentistry. The treatment of restoring teeth with ceramic inlays or onlays is a standard treatment in the internal clinic of Ivoclar Vivadent AG.

Postoperative sensitivities arise within days after the treatment. Therefore, the occurrence of postoperative sensitivities can be assessed already at baseline. Final assessment of postoperative hypersensitivities will be performed at the 1-month recall. If such an incident is still present after 1 month, it will be followed regularly.

The study duration of 5 years corresponds to the minimal duration recommended in restorative dentistry (Hickel et al., 2022). The patients will attend a recall after 6-12 days (baseline), 1, 6, 12, 24, 36, and 60 months.

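### Section 6.5 replaces treated participants who leave before the day 6-12 baseline recall, and no rule handles their missing hypersensitivity grade

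*Combined protocol and SAP*

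**What the plan says.** All references are to the combined protocol and SAP.

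- **Replacement (section 6.5).** "If a participant withdraws before all baseline examinations are completed, he/she will be replaced by another participant". The rule then ends: "Once all baseline examinations are completed, drop-outs are no longer replaced". Neither sentence mentions whether the adhesive has been placed or why the participant left. It is also unclear whether completion of baseline refers to one participant or to the whole cohort.
- **Timing (synopsis, Measurements and procedures).** "The baseline recall will take place 6-12 days after the insertion of the restoration". Baseline is therefore a post-treatment visit. The investigation schedule puts use of the adhesive at visit 3 (day 0), an optional visit 4 before baseline, and baseline at visit 5.
- **Onset (section 4.1).** "Postoperative sensitivities arise within days after the treatment".
- **First grading.** Section 3.1 says of hypersensitivity that "it is assessed for the first time at the baseline recall (after 6-12days".
- **Endpoint (synopsis, Outcomes).** "The primary endpoint of this clinical trial is the incidence rate of postoperative hypersensitivity". Section 6.4.2 tests the FDI 11 level with a Mann-Whitney test.
- **Analysis set (section 6.4.1).** "The data collected of all eligible participants that received a final restoration will be used for the statistical data analysis".

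Section 6.5 is headed as covering missing data, but it gives no imputation, worst-case or sensitivity rule.

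**The concern.** Replacing people who leave before they are exposed does no harm. Here the replacement window also covers the first 6-12 days of exposure, when the primary outcome is expected to appear. Pain in those days could itself make a participant leave. The treated tooth would then usually have no FDI 11 grade, and a newly treated tooth would make up the number.

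The plan records related information: adverse events from visit 2 onward, the optional visit 4, and a pre-baseline count of hypersensitive teeth in section 6.3. None of it is linked to the primary analysis.

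At stake is the rate that section 2.2 makes the primary objective, in a pivotal investigation run for conformity assessment. With only 45 teeth, one participant with two teeth is 2/45 = 4.4% of the planned sample.

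**Working it through.** **1. The plan's own figure.** Sections 6.2 and 6.5 give 40 + 5 = 45 restorations, an allowance of 5/45 = 11.1%. This reproduces. The 40 cannot be checked, because no effect size, control rate or margin is stated. Nothing below depends on it.

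**2. Sequence.** The adhesive is used on day 0, symptoms are expected within days, and the first scheduled grade comes on days 6-12. Replacement is allowed until that grade. The part of the window from day 0 to baseline is therefore after exposure and inside the outcome period.

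**3. Separating the missing grade from the replacement.** The plan gives no expected rate, so the counts are assumed: 45 teeth treated, 5 hypersensitive, and 2 of those 5 leave ungraded before baseline (for example, one participant with two teeth).

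| Handling | Calculation | Rate |
|---|---|---|
| True rate in the 45 | 5/45 | 11.1% |
| Graded teeth only, no replacement | 3/43 | 7.0% |
| Two symptom-free replacements | 3/45 | 6.7% |
| Two replacements at average risk | (3 + 2 × 5/45)/45 = 3.22/45 | 7.2% |

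The missing grades cost 11.1 − 7.0 = 4.1 points. Replacement moves the result by −0.3 points (7.0 to 6.7) or +0.2 points (7.0 to 7.2), depending on who the replacements are. It restores the count to 45, so the loss no longer shows in the number of graded teeth.

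**4. Direction.** Let p be the true rate, and let w1 and w0 be the probabilities that a symptomatic and a symptom-free tooth leave ungraded. The expected graded rate is

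p(1 − w1) / [p(1 − w1) + (1 − p)(1 − w0)].

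- **Only symptomatic teeth leave (w0 = 0).** For p = 10%, w1 = 25% gives 0.075/0.975 = 7.7%, and w1 = 50% gives 0.05/0.95 = 5.3%. For p = 20%, the same values give 0.15/0.95 = 15.8% and 0.10/0.90 = 11.1%.
- **Leaving is unrelated to symptoms (w1 = w0).** The factor cancels and the rate stays at p.
- **Only symptom-free teeth leave (w1 = 0).** The rate rises. For p = 10% and w0 = 10%, it is 0.10/(0.10 + 0.81) = 11.0%.

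All values of p, w1 and w0 are assumptions.

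**5. What full accounting would show.** In the example with two symptom-free replacements, 47 teeth received the adhesive. Counting the two ungraded teeth as non-events and then as events bounds the rate at 3/47 = 6.4% and 5/47 = 10.6%. If treated participants are not replaced, the bounds are 3/45 = 6.7% and 5/45 = 11.1%. If the pain was recorded before withdrawal, the upper figure is the observed one.

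**The case against.** The best counter-argument is that the missing grade, not the replacement, causes the bias. Step 3 confirms this. Restricting replacement alone would barely move the estimate, so a rule for the missing outcome has to come with it.

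The case against also notes that section 6.5 reports little loss in this clinic's earlier trials, and that patients in pain may well stay for care. Both are fair, and they make this a risk of unknown frequency. Section 6.3 counts FDI 11 grades before baseline, so some early grades may exist. That supports saying such teeth usually, rather than always, lack a grade.

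A reader might infer four stronger things that the documents do not support:

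- **The rule can only lower the rate.** Step 4 shows that the direction depends on who leaves.
- **Extra treated teeth will go unreported.** Section 6.4.1 takes in everyone with a final restoration, no passage limits reporting to 45, and adverse events are recorded from visit 2.
- **Participants already graded would be lost if completion of baseline means the whole cohort.** Section 6.4.1 keeps their data, so this is an ambiguity to settle and not a further bias.
- **The rule necessarily favours the result the sponsor expects.** A lowered test rate hides a true excess. If the true rates are equal, it moves the comparison away from no difference.

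Finally, section 6 says the methodology matches the earlier trial. If its control arm was handled in the same way, which the documents do not say, the comparison may be partly protected. The test-adhesive rate itself would not be.

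**Conclusion.** The point holds as a gap between sections 6.4.1 and 6.5. Replacement is permitted after exposure and inside the outcome window, and a treated tooth that leaves ungraded stays in the analysis set only in name. If withdrawal is related to symptoms, the test-adhesive rate is biased downward. In the assumed example it falls from 11.1% to between 6.7% and 7.2%, almost all of it through the missing grades. If withdrawal is unrelated to symptoms, the expected rate is unchanged.

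The size rests entirely on assumed event counts and withdrawal behaviour, and no bias has been demonstrated. The gap is still worth closing before the primary analysis, because a tooth that was never graded cannot be graded afterwards.

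**What to change.** - **Section 6.5.** Replace only participants who withdraw before the adhesive is applied. State that completion of baseline is judged per participant.
- **Section 6.4.1.** Keep every tooth that received the adhesive in the denominator of the primary incidence rate.
- **Missing FDI 11 grade.** Classify the tooth from any hypersensitivity recorded before withdrawal (adverse-event record, optional visit 4). State in advance how a tooth with nothing recorded is classified.
- **Sensitivity analysis.** Count all treated teeth without a grade as events in the rate, and give them the worst rank in the Mann-Whitney test. Calling a tooth an event supplies no grade, so the test needs its own rule.
- **Reporting.** Give the number of teeth treated, and the number of withdrawals with timing and reason.
- **Historical control.** Apply the same handling to the control data where they allow it, so that the change does not create a new difference between the groups.

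The cost is a wording change in two sections and slightly more analysis work. A few treated teeth may lack a grade, which the allowance of 5 restorations can absorb. The reported rate may be less favourable.
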